#### **A. SPECIFIC AIMS**

The specific aim of this study is to address the significant gap in the evidence base for metformin (MET) use in overweight and obese youth with Bipolar Spectrum Disorders (BSD).

The overall objective of this prospective, large, PRAGMATIC randomized trial is to study the impact of MET and healthy lifestyle intervention (LIFE) vs. LIFE alone on patient-centered outcomes of body weight, Second Generation Antipsychotics (SGA) adherence and satisfaction, psychiatric symptom burden (e.g. mood/anxiety), and quality of life (QoL). We will also examine metabolic outcomes.

**Specific Aim 1:** Assess the overall and subgroup-specific impact of MET+LIFE versus LIFE alone on short- (6mo) and long-term (24mo) **weight and metabolic health** in overweight and obese youth with BSD.

**H1.1:** Overall, assignment to treatment with MET will abrogate more weight gain and lead to fewer adverse metabolic outcomes than LIFE alone at 6 and 24 months.

**H1.2:** (Heterogeneity of Treatment Effects [HTE]): MET's effectiveness at abrogating weight gain and components of metabolic syndrome will vary with respect to the following factors (see Patient Population and Background for rationale and prior data): 1) Change in BMI z-score from SGA initiation to baseline (in patients already receiving SGA treatment); 2) Prior exposure to and duration of SGA treatment; 3) Baseline BMI z- score; 4) Baseline psychotropic weight burden (in SGA non-naïve patients; as defined in Measures below); 5) BSD as diagnosed by a structured interview; 6) Age; 7) Type of insurance (public/private); 8) Ethnicity (Hispanic/Non); 9) Baseline insulin resistance (HOMA-IR); 10) Race (African-American (AA) vs non-AA).

**Specific Aim 2:** Assess the overall and subgroup-specific impact of MET+LIFE vs. LIFE alone on short- (6mo) and long-term (24mo) **SGA adherence and treatment satisfaction**, including assessment of how these effects may be mediated by MET effects on weight gain.

**H2.1:** Overall, assignment to treatment with MET will lead to better SGA adherence and greater treatment satisfaction than LIFE alone after both 6 and 24 months.

**H2.2:** (HTE): MET effectiveness with regard to SGA adherence will vary with respect to: 1) Baseline weight acceptability; 2) Baseline psychotropic medication treatment acceptability; 3) Type of insurance (public/private).

**H2.3:** The overall effects of MET treatment on SGA adherence will be mediated by degree of weight abrogation, and this relationship will be stronger among girls than boys. We anticipate a possibly complex relationship between abrogation of weight gain (associated with MET) and SGA adherence, because weight gain may also be avoided via SGA non-adherence (at the probable cost of sub-optimal psychiatric outcomes; see Specific Aim 3). A statistical framework (marginal structural models) to accommodate this possibility is described in the Statistical Analysis Plan.

**Specific Aim 3:** Assess the overall and subgroup-specific impact of MET+LIFE vs. LIFE alone on **psychiatric symptom burden, psychotropic treatment changes, and overall and weight-related QoL**, including assessment of how these effects are mediated by MET effects on weight gain and SGA adherence.

**H3.1:** Overall, assignment to treatment with MET will be associated with lower psychiatric symptom burden, decreased risk for symptom-driven treatment changes, and greater improvements in overall and weight-related QoL than LIFE alone at both 6 and 24 months, post-randomization.

**H3.2:** (HTE): MET effects on psychiatric symptoms will be smaller in patients who meet full DSM criteria for a BSD.

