## **E. EXPERIMENTAL DESIGN & METHODS**

### **a. Methods and Procedures**

**Study Overview:** We propose a prospective, large, PRAGMATIC, randomized trial to study the impact of MET and healthy lifestyle intervention (LIFE) vs. LIFE alone on patient-centered outcomes of body weight, SGA-adherence and satisfaction, psychiatric symptom burden (e.g. mood/anxiety), and QoL. We will also examine metabolic outcomes.

The focus of the pragmatic trial is to determine which intervention is most effective through observation of care as usual conditions or in “real-world clinical settings” rather than under controlled experimental circumstances. Information should be collected when available as part of routine clinical practice rather than through study-specific procedures, with minimal interference to clinical practice. Adherence to protocol recommendations from practitioners and patients are observed and documented throughout the study.

**Subjects:** We propose to recruit approximately 1800 overweight/obese youth with BSD who are prescribed SGAs from at least 40 public and private mental health practices (approximately 900 each from sites under the coordination of University of Cincinnati, Midwestern center and from within the sites under the Northwell Health East Coast coordinating center), to participate in the proposed patient-centered large pragmatic trial examining the effectiveness of MET and LIFE vs. LIFE alone. Patients will be eligible for study participation if they are:

1. Inpatient or outpatient age 8-19 years inclusive; participants must live with a parent, guardian, or caregiver;
2. Fluent in English;
3. Diagnosed or told by a clinician that they have any of the following bipolar spectrum disorders (BSD): bipolar I, bipolar II, unspecified bipolar and related disorders, Disruptive Mood Dysregulation Disorder (DMDD), cyclothymic disorder, other specified bipolar and related disorders, as well as mood disorder not otherwise specified (if diagnosed in the past as per DSM-IV);
4. Body mass index  $\geq 85\text{th}$  percentile for age and sex by standard growth charts;
5. Received a new or ongoing prescription for at least one SGA (i.e., olanzapine, clozapine, risperidone, quetiapine, aripiprazole, ziprasidone, iloperidone, lurasidone, paliperidone, brexpiprazole or cariprazine) that is not prescribed as a PRN medication

Additionally, patients will be excluded by the following:

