## **OUTCOME MEASURES:**

Due to MOBILITY being a pragmatic and largely observational study, any participant who is deemed eligible by the above criteria will be enrolled in MOBILITY. These criteria, along with providing appropriate informed consent/assent, are the necessary criteria for participation in MOBILITY. We will continue to collect data in a naturalistic manner from all patients who have met these criteria regardless of whether they begin the intervention to which they have been randomized or have not attended all of their clinical follow up appointments. Patients will have follow-up study visits and data collected concurrent with their existing CLINICAL visit schedule.

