for data entry and real time validation (e.g., automated data type and range checks); 2) HIPAA-compliant and 21 CFR Part 11-ready audit trails for tracking data manipulation and exports; 3) record locking and electronic signature functions; 4) control of view/edit rights; 5) a tool for reporting, monitoring and querying patient records; and 6) automated export to common statistical packages. REDCap is hosted on a network specially designed to support the rigorous security and compliance requirements of clinical research projects. Administered by the CCHMC Division of Biomedical Informatics, this network features multiple firewalls and a central facility for managing hosted systems and users, creating another layer of access control and audit capability on top of what REDCap already provides (e.g., user access can be monitored and controlled at the network level without making any changes within REDCap itself). These capabilities are available to authorized network administrators and REDCap study owners only, and user access changes are documented by an audit trail. The data management team will monitor the database throughout the study to assure that data are complete and accurate.

**Analyses of Specific Aims:** Each specific aim involves assessment of domains that are hypothesized to be affected by MET either directly or indirectly through other domains. Our approach to potential HTE distinguishes effect moderators from mediators of distal outcomes. Moderators include fixed patient characteristics and pre-treatment covariates values. Mediators include variables that are hypothesized to be affected by MET treatment and that may in turn affect other outcomes. We will utilize generalized linear mixed models (GLMM), which allow for outcomes from a range of distributions and will include random effects to account for unspecified causes of variation among sites and patients, and subgroup-specific coefficients to assess HTE.

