The basic model for outcomes will be a GLMM with change from baseline to either 6- or 24- months as the dependent variable. Independent variables will include fixed-effect terms for randomized treatment group (MET), baseline value of the outcome, and random site effects. For HTE analyses, a baseline value-by-MET interaction (to assess HTE due to baseline status) will be included, and for particular domains additional continuous or categorical covariates and treatment-by-covariate interaction terms will be added to assess HTE. Outcomes within each domain will share the same set of HTE terms, specified in the Specific Aims. Because the subgroups are in general correlated (e.g., duration of SGA treatment, weight gain history and psychotropic weight burden will be correlated with baseline BMI), we will include multiple first-order HTE terms simultaneously (to assess heterogeneity independently attributable to each moderator), but will also fit separate models for each term to gauge the impact of this correlation on our conclusions. Higher-order treatment-by-covariate interactions will not be included a priori, but will be explored with rigorous adjustment for multiple testing, using step-down testing (removing highest-order interaction terms first) or information criteria based on penalized likelihoods to guide model selection.

**Marginal Structural Modeling for Causal Inference:** SA1 concerns the overall and sub-group specific effects of MET on abrogation of weight gain (with changes in BMI z-score from baseline as outcomes) and metabolic health, particularly metabolic syndrome and its component criteria. BMI and adherence measures are obtained at all study visits, so our models for these measures will use all available observations by treating the longitudinal series of changes in these variables and SGA treatment as dynamically dependent on each other. We will use marginal structural models to address this bi-directional dependence, computing the probability of SGA treatment regimen change at each visit within weight gain treatment regimen groups and using appropriately normalized versions of the inverse of the probability as the stabilized weights.

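### The HTE models specify no MET-by-site effect and no within/between-site split, so the insurance interaction (less so ethnicity and race) may have too small a standard error and may partly reflect the practice

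*Combined protocol and SAP*

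**What the plan says.** Section A, H1.2, names ten factors expected to modify MET's effect on weight and metabolic outcomes. Items 7 and 8 read "7) Type of insurance (public/private); 8) Ethnicity (Hispanic/Non", and item 10 is race (African-American or not). H2.2 repeats insurance for SGA adherence: "3) Type of insurance (public/private".

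Section E.b, Analyses of Specific Aims, describes mixed models that "will include random effects to account for unspecified causes of variation among sites and patients". The basic model is given as: "Independent variables will include fixed-effect terms for randomized treatment group (MET), baseline value of the outcome, and random site effects". For HTE, "treatment-by-covariate interaction terms will be added to assess HTE". Several moderators are entered together, "to assess heterogeneity independently attributable to each moderator".

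Section E.a says recruitment is "from at least 40 public and private mental health practices", in two regions. Randomization is 1:1, stratified by site, weight class, prior SGA exposure and sex, and not by insurance, race or ethnicity. Nothing in the documents names a MET-by-site term, site-clustered standard errors, or a division of a moderator into its site mean and the patient's departure from it.

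**The concern.** Because randomization is stratified by site, an additive site effect largely cancels out of the MET contrast. It adjusts for sites whose patients gain more or less weight overall. It does not adjust for sites where assignment to MET works better or worse.

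The design leaves room for such differences. Data are collected "regardless of whether they begin the intervention to which they have been randomized", the titration is a recommendation, and clinicians may start MET outside the assignment after an initial period or add it in the LIFE arm. How much MET each arm receives can therefore vary by practice.

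Two separate problems can follow if a moderator is unevenly spread over practices:

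- **Precision.** If MET's effect varies between sites for reasons unrelated to their patient mix, the interaction estimate is unbiased but its standard error is too small.
- **Attribution.** If MET's effect varies with the patient mix (for example, practices with mostly publicly insured patients deliver less of it), the interaction credits the patient's insurance with what belongs to the practice.

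At stake is a published statement that publicly insured, Hispanic or African-American youth respond differently to MET when the difference lies in how their practices deliver it.

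**Working it through.** The documents give no alpha for the HTE tests, no between-site variance of MET's effect and no per-site insurance shares. There is therefore no planned error rate to reproduce, and the size has to be shown over assumed ranges.

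**Inputs from the documents**

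- 1800 patients and 40 sites, so m = 1800/40 = 45 per site; 1:1 allocation (sections E.a, F.b).
- Effect scale: 24-week BMI z change of −0.088 with MET and +0.040 in control in the prior three-arm trial (section C). The difference is 0.040 + 0.088 = 0.128 z.
- Residual SD σ = 0.5 z, reading the pilot's figure of 0.27 and 0.5 in section C as a mean and an SD.
- Study-wide shares of 20% Black and 15% Hispanic (section F.d).

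**Assumptions**

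- Two-sided 5% test and no true interaction.
- Half the sites are mainly public and half mainly private. 90/10 means 90% of patients at the first kind, and 10% at the second, are publicly insured.

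Let v be the overall variance of the moderator and ρ the share of v lying between sites. For 90/10, v = 0.25 and ρ = (0.4)²/0.25 = 0.64. For 70/30, ρ = (0.2)²/0.25 = 0.16.

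**1. Random site variation in MET's effect, SD τ, unrelated to composition.** The true variance of the interaction estimate exceeds the model's by the factor 1 + ρ·m·τ²/(4σ²). Type I error is 2[1 − Φ(1.96/√factor)].

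| Shares | τ | Factor | Type I error |
|---|---|---|---|
| 90/10 | 0.05 | 1 + 0.64·45·0.0025 = 1.072 | 5.8% |
| 90/10 | 0.10 | 1 + 0.64·45·0.01 = 1.288 | 8.4% |
| 70/30 | 0.05 | 1.018 | 5.2% |
| 70/30 | 0.10 | 1.072 | 5.8% |

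Simulation at 90/10 gave 6.3% and 8.7%; at 70/30 it gave 4.7–5.9%. With τ = 0 or ρ = 0 the factor is 1. Simulated rates there were 4.3–6.1%, with Monte Carlo error of about 0.5 points.

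**2. Site effects that track composition.** Suppose public practices deliver 60% of the effect and private practices all of it, with no insurance effect within a practice. The practice gap is 0.4 × 0.128 = 0.051 z. The planned interaction picks up the fraction (difference in shares)/(4v) of it:

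- 90/10: 0.8/(4·0.25) = 0.80, giving 0.041 z.
- 70/30: 0.4/(4·0.25) = 0.40, giving 0.020 z.

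The model's standard error is σ/√(1800·0.25·v) = 0.5/√112.5 = 0.047. The rejection rate is Φ(−1.96 + z) + Φ(−1.96 − z), with z = bias/SE.

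- 90/10: z = 0.87, rejection 14.0% (simulated 13–14%).
- 70/30: z = 0.43, rejection 7.2% (simulated 7.4–8%).

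At a smaller σ of 0.3 the corresponding rates are about 30% and 11%.

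**3. Race-like moderator.** With assumed site shares of 30/10 (20% overall, v = 0.16) and the same gap, the fraction is 0.2/(4·0.16) = 0.31. The bias is 0.016 z, the SE 0.059, and rejection 5.8% (simulated about 5–6%).

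**4. What each remedy does.** A separate simulation used 40 unequal sites, σ = 0.5 and ρ = 0.3, with site effects correlated 0.5 with site share.

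| Model | τ = 0.064 | τ = 0.128 |
|---|---|---|
| Random site intercept only | 11.1% | 28.9% |
| Plus random MET-by-site slope | 8.7% | 14.0% |
| Plus within/between split (within-site term) | 5.0% | 4.9% |

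The slope mainly repairs the standard error. Only the split removes the misattribution.

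**5. Cost of the split.** The within-site estimate uses only the fraction 1 − ρ of the moderator's variance, so its SE is multiplied by 1/√(1 − ρ): 1/√0.84 = 1.09 at 70/30 and 1/√0.36 = 1.67 at 90/10.

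**The case against.** Five points can be made for the plan.

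- **Clustering is not documented.** The text calls practices public and private, which is not the same as the payer of each patient. For race and ethnicity it gives study-wide shares only. This stands: clustering is a reasonable inference for insurance and a weaker one for the other two.
- **The random effects may be wider than an intercept.** The plan says random site effects and never says intercept. An intercept is the natural reading, but the supportable statement is that no MET-by-site effect is specified.
- **Delivery is partly standardized.** Titration is common, site staff are trained, and the lifestyle video is the same everywhere. Patients given MET outside their assignment are to be placed in a separate analytic group. This could limit site variation, but the plan does not say how that group enters the HTE models.
- **The phrase about independent attribution concerns other things.** It addresses correlation among the listed moderators, such as SGA duration and baseline BMI, and promises nothing about practice. That is correct, so the plan does not contradict itself here.
- **Variation through practices may be part of the question.** In a pragmatic trial, H1.2 can fairly ask whether effectiveness differs by insurance by whatever route. This also stands. Resting H1.2 on the within-site term alone would change the estimand and cost precision, so the planned interaction should remain.

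A reader might go further and infer that these tests do reject too often, or that any insurance or race difference found will be a practice artefact. The documents support neither. Both depend on two quantities that are not given, and with either near zero the test is close to nominal.

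**Conclusion.** The concern holds as a conditional gap in specification. The HTE models name no MET-by-site effect and no within/between-site separation for moderators that may well differ between practices, in a design that leaves MET delivery largely to clinicians.

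For insurance, at σ = 0.5 z, the assumed scenarios give about 6–9% false positives from random site variation (90/10 shares) and about 8–14% from composition-related variation (70/30 to 90/10 shares). Rates near 30% need both 90/10 shares and a residual SD of 0.3, which is smaller than the pilot's figure, so they should not be read as the expected size. For race and ethnicity the inflation is slight at weak clustering. The site shares, the site variation and the 60% delivery figure are assumptions, not trial data. The analysis of the overall MET effect is not put in question by this point.

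**What to change.** In the HTE models for insurance, ethnicity and race (H1.2 items 7, 8 and 10; H2.2 item 3), specify before analysis:

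1. A random MET-by-site slope, or site-clustered standard errors, with degrees of freedom suited to about 40 sites.
2. Alongside the planned overall interaction, two further terms: MET by the patient's departure from the site mean, and MET by the site mean.
3. A reporting rule: describe a difference as belonging to the patient characteristic only if the within-site estimate is consistent with it, and report the site-mean term as a difference between practices.

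This needs no new data and leaves the overall-effect model as it is. The cost is somewhat wider intervals for these interactions and an imprecise within-site estimate where practices are nearly all public or all private (SE about 1.1 times larger at 70/30 shares and 1.7 times at 90/10).

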1. Patients will be excluded if they have had exposure to a total daily dose of MET 1000 mg bid for at least 2 weeks in the past 3 months;
2. Patients will be excluded if they could not tolerate MET during the recommended titration schedule outlined in the protocol;
3. Major neurological or medical illnesses that affect weight gain (e.g., unstable thyroid disease) or require a systemic medication that might impact weight or glucose regulation (e.g., diabetes mellitus [insulin], chronic renal failure [steroids]);
4. If lab results are available in the last 6 months, then a fasting serum glucose  $\geq 126 \text{ mg/dL}$  on two occasions prior to or during screening, indicating need for prompt treatment.
5. If lab results are available in the last 6 months, then a serum creatinine  $\geq 1.3 \text{ mg/dL}$  on two occasions during screening and/or follow-up, indicating potential impairment of renal functioning
6. Pregnant or breast feeding;
7. Based on their clinician's assessment, children and caregivers who are unable to complete screening/baseline assessments for any reason;

The enrollment rate will be approximately 1-2 patients/month/site for a recruitment time of 57 months.

**Randomization:** We will randomize 1800 patients (1:1 ratio) to either MET + LIFE or LIFE alone. All patients will receive a lifestyle intervention (LIFE) of brief standardized education. Once a patient is determined to meet the above criteria and has provided appropriate informed consent/assent, site staff will assign the participant a patient ID number. The site staff will then log on to the study's REDCap site and enter the Patient ID, and the following stratification factors: site, overweight or obese, previous SGA exposure, and sex of patient (transgendered patients will be randomized according to sex assigned at birth). REDCap has a built in mechanism that prevents duplication of subject ID numbers.

Once all stratification factors have been entered, the REDCap randomization module will return the next assignment for the appropriate strata.

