### **Adherence and Treatment Satisfaction Outcomes:**

**Self-Reported Adherence and Barriers:** Caregivers and children will answer standardized questions related to adherence and adherence barriers to taking SGAs, MET (if applicable), and LIFE. Information on missed and partial doses of each medication in the past week will be ascertained. Questions prefaced by non-judgmental language that normalizes non-adherence to treatment will be used. A time period of one week will be used to maximize respondent recall and minimize memory decay.

**MEMS®6 TrackCap/SimpleMed PillBox:** The Medication Event Monitoring Systems (MEMS) [AARDEX Corporation] and the SimpleMED PillBox are electronic monitoring systems that measure the dosing histories of oral medications. They will be used to monitor adherence to SGAs or MET in a sub-sample of 300 patients at a subset of sites. They consist of a standard plastic vial or box with a threaded opening and a closure for the vial that contains a micro-electronic circuit to register the dates and times the bottle/pillbox is opened and closed. Data from the MEMS TrackCap will be downloaded at each study visit. Patients randomized at an inpatient site to MEMS monitoring will only receive this monitoring if they are scheduled to be followed at an outpatient site that was selected for MEMS monitoring; otherwise, the MEMS aspect of the randomization should be disregarded.

**Treatment Acceptability:** A single-item 5-category Likert-type patient report of satisfaction with psychotropic medication regimen (0=not at all satisfied to 4=very satisfied).

**International Physical Activity Questionnaires (IPAQ):** The IPAQ is an instrument for cross-national monitoring of physical activity and inactivity with good reliability and validity for monitoring population levels of physical activity in diverse settings to assess adherence to LIFE physical activity recommendations.

We will also assess food choices and eating habits using questions selected from the Healthworks Nutrition Screener, Satiety and Food Responsiveness using items from the Child Eating Behavior Questionnaire, and Uncontrolled Eating and Cognitive Restraint using items from the 3-factor Eating Questionnaire.

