**Adjustment of Self-Reported Adherence:** Adherence rates for self-report and MEMS (where available) will be calculated as number of treatments/day divided by number of prescribed daily treatments. Truncated MEMs adherence rates (maximum of 100%) will be used in analyses to reduce inflation as a result of overuse or extra openings due to prescription refills. This method has been used successfully in studies assessing electronic monitoring (EM) adherence. Self-reported adherence vastly underestimates adherence as measured by EM. While it is not feasible to use EM for all patients and medications, we will use the statistical relationship between EM and self-reported adherence in a subsample of 300 patients (equal numbers per treatment group, i.e., 100 for SGA adherence who are also taking MET, 100 for SGA adherence who are not taking MET, and 100 for MET adherence, who are

randomly selected the 8 randomization strata) to estimate EM adherence from self-report in the remaining patients. We will regress EM adherence on self-reports, using standard diagnostics to ensure that non-linearity, heterogeneity of variance across the range of adherence, or subgroup-specific regression relationships are included as needed. Predictions that accurately reflect the residual uncertainty can then be generated by multiple imputation, and the resulting complete-sample datasets will be used in primary analyses involving SGA adherence, with sensitivity assessed by parallel analyses using self-report directly.

**Data and Safety Monitoring plan:** The Cincinnati site will provide an independent certified study data monitor who will visit each site prior to study initiation and approximately every 6 months thereafter. The monitor will follow a monitoring plan that includes source data verifying and ensuring compliance with good clinical practices (GCPs), the IRB-approved protocol and other applicable regulatory guidelines, and will report any problems to the site PI and the other clinical staff members. Additionally, adherence to inclusion/exclusion criteria, completion of scheduled assessments, withdrawal/termination procedures, and maintenance of training and certification for all research personnel will be continuously monitored. The monitor will provide written recommendations following each visit to each site. All reports will be reviewed by members of the Steering Committee.

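### The imputation model for electronically measured SGA adherence names only self-report, so used as written it would weaken the weight-to-adherence and adherence-to-symptom paths that H2.3 and Aim 3 are meant to estimate

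*Combined protocol and SAP*

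**What the plan says.** Section A (Specific Aims) gives SGA adherence two roles in mediation. In H2.3 it is the outcome: "The overall effects of MET treatment on SGA adherence will be mediated by degree of weight abrogation", with a stronger relationship expected in girls. In Aim 3 it is a mediator: "including assessment of how these effects are mediated by MET effects on weight gain and SGA adherence".

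Section E.a sets the sample: "We will randomize 1800 patients (1:1 ratio) to either MET + LIFE or LIFE alone". Under Adherence and Treatment Satisfaction Outcomes, electronic devices are limited to a subset: "They will be used to monitor adherence to SGAs or MET in a sub-sample of 300 patients at a subset of sites". Section E.b, Adjustment of Self-Reported Adherence, splits that subset: "100 for SGA adherence who are also taking MET, 100 for SGA adherence who are not taking MET, and 100 for MET adherence".

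The same paragraph says the relationship found in the subset will be used "to estimate EM adherence from self-report in the remaining patients". The method is: "We will regress EM adherence on self-reports, using standard diagnostics". The diagnostics cover non-linearity, unequal variance and subgroup-specific relationships, added where needed. Values are then drawn by multiple imputation so that they carry residual uncertainty, and "the resulting complete-sample datasets will be used in primary analyses involving SGA adherence". A parallel analysis uses raw self-report as the sensitivity check.

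No section names arm, BMI z change or any Aim 3 outcome as a predictor in this imputation. None expressly excludes them.

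**The concern.** Multiple imputation preserves an association only if the imputation model contains the variables that the analysis will relate to the imputed one. Here the only named predictor is self-report. An imputed adherence value is then a self-report signal plus random noise. Given self-report, it has no connection with the patient's weight change or symptoms.

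That would be minor if few values were imputed, but about eight in nine are. The trial could then report that weight does not drive adherence, or that adherence does not carry metformin's effect on symptoms, because of the imputation step alone. A larger sample would not help, because the bias depends on the monitored fraction and on how well self-report tracks EM adherence. The listed diagnostics examine the fit of EM on self-report and would not reveal it.

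**Working it through.** **Counts (Section E.b).** The subset reproduces: 100 + 100 + 100 = 300. Of these, 100 + 100 = 200 have SGA adherence measured electronically. Imputed: 1800 - 200 = 1600, and 1600/1800 = 88.9%. Some inpatients selected for monitoring will not receive it, so 200 is an upper limit unless they are replaced.

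**Assumption.** The documents give no correlation r between EM and self-reported adherence. I take r = 0.3 to 0.7 as illustration and also show 0.8 and 0.9.

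**Closed form.** Standardise EM adherence E and self-report S, and suppose S relates to weight change W only through E. The imputed value is E* = rS + noise. Then cov(E*, W) = r x cov(S, W) = r x r x cov(E, W), so the imputed patients keep r² of the association. Pooled over monitored and imputed patients, the share kept is (200 + 1600r²)/1800:

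- r = 0.3: (200 + 144)/1800 = 19%
- r = 0.5: (200 + 400)/1800 = 33%
- r = 0.7: (200 + 784)/1800 = 55%
- r = 0.8: (200 + 1024)/1800 = 68%
- r = 0.9: (200 + 1296)/1800 = 83%

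**Simulation.** 400 trials per scenario, n = 1800, 100 monitored per arm, 5 proper normal imputations. Assumed paths: MET to weight -0.3, weight to adherence -0.3, direct MET to adherence 0.2, adherence to symptoms -0.3. The adherence-to-symptom path is adjusted for arm and weight. Entries are the share of the true value kept.

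| Imputation model | r | Weight to adherence | Adherence to symptoms | MET to adherence (total) |
|---|---|---|---|---|
| Self-report only | 0.3 | 19% | 17% | 19% |
| | 0.5 | 34% | 30% | 34% |
| | 0.7 | 54% | 51% | 55% |
| | 0.8 | 68% | 63% | 68% |
| + arm | 0.3 | 19% | 17% | 98% |
| | 0.7 | 54% | 51% | 101% |
| + arm, weight change, outcome | 0.3 | 100% | 101% | 103% |
| | 0.7 | 101% | 99% | 103% |

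Adding arm repairs the treatment effect on adherence but neither mediation path. Adding weight change and the outcome repairs both. The product MET to adherence to symptoms keeps 3% (r = 0.3) to 28% (r = 0.7) with self-report only, and 17% to 51% with arm added.

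**Differential reporting.** When self-report was also made to depend directly on symptoms, in either direction, adherence-to-symptoms ranged from 2% to 123% of truth and weight-to-adherence from 15% to 62%.

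**Raw self-report analysis.** Take self-report as EM adherence plus independent error on the same scale.

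- *Weight to adherence.* Adherence is the outcome, and random error in an outcome does not bias the unstandardised slope. Simulated values were 99-103% of truth.
- *Adherence to symptoms.* Adherence is now the predictor. Its variance given arm and weight is 1 - 0.09 = 0.91. Its total variance is about 0.91 + 0.09 + 0.29²/4 = 1.02, where 0.29 = 0.2 + 0.3 x 0.3 is the total MET effect. The error variance is therefore 1.02 x (1/r² - 1). The share kept is 0.91/(0.91 + error variance): 8%, 23% and 46% at r = 0.3, 0.5 and 0.7.

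**The case against.** Four points can be made for the plan.

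- **The paragraph is a short description, not a full model.** It allows subgroup-specific relationships, and the marginal structural modelling paragraph treats BMI and adherence as depending on each other over time. It is therefore fair to say only that the variables are not named; a reader might infer that they are ruled out, and the text does not say so. But the subgroup clause lets the EM/self-report relation differ between groups and does not bring in post-baseline weight or symptoms. The structural models weight for changes in SGA regimen, which does not restore a covariance lost in imputation.
- **The correlation could be high.** Caregiver and child both report, covering missed and partial doses, at baseline and up to ten later visits. A pooled predictor may track EM adherence better than a single report. This stands, so 17-55% must not be read as a property of the plan. Nor do the documents show that at least half of each path is lost: at r = 0.7 slightly more than half is kept.
- **There is a sensitivity analysis.** A reader might infer that it shares the attenuation. For H2.3 that is wrong: under simple random error it is close to unbiased. For adherence-to-symptoms it is attenuated at least as much as the imputed analysis, so it does not protect Aim 3.
- **The reach is limited.** The primary outcome is BMI z-score, and its main comparison uses no adherence data. If arm is in the imputation model, the H2.1 adherence contrast is also intact.

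**Conclusion.** The concern holds as a flaw in a stated method, confined to analyses that use imputed SGA adherence. Followed as written, the imputation pulls the weight-to-adherence and adherence-to-symptom paths towards zero when reporting error is unrelated to weight and symptoms. The size is conditional: about 17-55% of each path kept for an assumed correlation of 0.3-0.7, about 63-68% at 0.8, and more above that. These figures describe single paths; the full indirect effect through adherence shrinks further if arm is also left out.

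The direction is not guaranteed. If reporting depends on symptoms, the adherence-to-symptom path can be overstated as well as understated.

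For H2.3 the primary and sensitivity analyses may disagree, with the primary one wrong. The near-unbiased result for raw self-report assumes additive random error on the EM scale. The plan's statement that self-report runs well below EM adherence would leave that slope unchanged if the shortfall is constant, but would rescale it if proportional.

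**What to change.** In Section E.b, Adjustment of Self-Reported Adherence, state that the EM imputation model contains:

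- self-report;
- randomised arm;
- BMI z change at the same and earlier visits;
- the Aim 3 outcome being analysed;
- for H2.3, the interaction of BMI z change with sex, since that hypothesis compares girls with boys. The simulation did not cover this term; the case for it is the same argument.

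Use these datasets for H2.3 and the Aim 3 mediation. Report both analyses in the EM-monitored patients alone as a check. Report the observed EM/self-report correlation, so that readers can judge how much the imputed values depend on the model. Say also how the raw self-report analysis should be read on each path: informative for weight-to-adherence, not corrective for adherence-to-symptoms.

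The cost is a sentence or two in the plan and a larger imputation model, with no new data or visits. The downside is wider intervals, because at most about 200 patients inform the added terms. For that reason it is better to impute separately for each outcome analysed than to load every Aim 3 measure into one model.
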